### **5.2.3. Dosage and Administration of SOF**

PK Lead-in: (Cohort 1) SOF 400 mg tablets will be administered once daily along with RBV weight-based dosing. Subjects determined unable to swallow the placebo for the 400 mg SOF tablet (by SOF Placebo swallowability assessment at Screening up to Day 1) will be re-assigned to 4 x 100 mg tablets daily. Subjects unable to swallow tablets will be re-assigned to 8 x 50 mg capsules containing granules. Subjects who weigh < 45 kg will be excluded.

PK Lead-in: (Cohort 2) SOF 200mg (2 x 100 mg tablets) will be administered once daily along with RBV weight-based dosing. Subjects determined unable to swallow the placebo for the 100 mg SOF tablet (by SOF Placebo swallowability assessment at Screening up to Day 1) will be re-assigned to 4 X 50 mg capsules containing granules. Subjects who weigh outside of the  $\geq 17$ kg and < 45 kg range will be excluded

PK Lead-in: (Cohort 3) subjects weighing  $\geq 17$  kg will receive 200 mg SOF (4 x 50 mg capsules containing granules) + RBV weight-based dosing for 7 days. Subjects who weigh <17 kg will receive 150 mg SOF (3 x 50 mg capsules containing granules) + RBV weight-based dosing for 7 days.

Intensive PK and safety results from the PK Lead-In of each Cohort will be reviewed to confirm the appropriateness of the evaluated SOF dose for the Treatment Phase of that Cohort as well as to determine the age-appropriate dose to be evaluated in the PK Lead-in of the next Cohort.

Treatment Phase: Subjects who participated in the PK Lead-in of each Cohort will continue in the Treatment Phase with no interruption of study drug administration until the appropriateness of the dose is confirmed by PK and safety data from the PK-Lead-in. Additional subjects will be enrolled in the Treatment Phase of each Cohort upon confirmation of the appropriateness of the dose.

## **5.3. Ribavirin**

### **5.3.1. Description and Handling of RBV**

#### **5.3.1.1. Formulation**

REBETOL capsules consist of a white powder in a white, opaque, gelatin capsule. Each capsule contains 200 mg ribavirin and the inactive ingredients microcrystalline cellulose, lactose monohydrate (40 mg), croscarmellose sodium, and magnesium stearate. The capsule shell contains gelatin, titanium dioxide. The capsule shell imprint contains shellac, propylene glycol, ammonium hydroxide, coloring agent (E 132). The hard capsule is imprinted with blue ink.

REBETOL RBV Oral Solution 40 mg per mL is a clear, colorless to pale or light yellow bubble gum-flavored liquid. In addition to the active ingredient, RBV oral solution contains the

following inactive ingredients: sucrose, glycerin, sorbitol, propylene glycol, sodium citrate, citric acid, sodium benzoate, natural and artificial flavor for bubble gum #15864, and water.

### 5.3.1.2. Packaging and Labeling

The RBV capsules are packaged in blisters. Each blister card contains 20 capsules and seven cards (140 capsules) per carton.

The RBV oral solution is packaged in 4-oz amber glass bottles (100 mL/bottle) with child-resistant closures.

RBV capsules and oral solution to be distributed to centers in the US, EU and the rest of the countries shall be labeled to meet all applicable requirements of the US Food and Drug Administration (FDA) and Annex 13 of Good Manufacturing Practices: Manufacture of investigational medicinal products (February 2010) and/or other local regulations as applicable.

### 5.3.1.3. Storage and Handling

RBV capsules should not be stored above 30 °C (86 °F).

RBV oral solution should not be stored above 30°C (86°F).

## 5.3.2. Dosage and Administration of RBV

RBV dose will be administered by weight as follows:

Body Weight kg (lbs.)	RBV Daily Dose	RBV Number of Capsules
<47 (<103)	15 mg/kg/day	Use Oral Solution. Divided dose in the morning and evening.
47-49 (103-108)	600 mg/day	1 x 200-mg capsules A.M. 2 x 200-mg capsules P.M.
50-65 (110 – 143)	800 mg/day	2 x 200-mg capsules A.M. 2 x 200-mg capsules P.M.
66-80 (145 – 176)	1000 mg/day	2 x 200-mg capsules A.M. 3 x 200-mg capsules P.M.
81-105 (178-231)	1200 mg/day	3 x 200-mg capsules A.M. 3 x 200-mg capsules P.M.
>105 (>231)	1400 mg/day	3 x 200-mg capsules A.M. 4 x 200-mg capsules P.M.

\* Note: Subjects with a body weight greater than or equal to 47 kg may utilize the RBV oral solution if necessary.

The morning dose of RBV will be taken with food and SOF. The evening dose of RBV will be taken with food.

RBV will be supplied by Gilead Sciences for all subjects.

#### **5.4. Co-administration of SOF and RBV**

In the Treatment Phase of the study, each subject will be given instructions to maintain approximately the same daily dosing interval between study drug doses.

For **morning doses**, subjects will be instructed to take study drugs as follows:

- SOF
- Weight-based RBV (as per Section 5.3.2).

For **evening doses**, subjects will be instructed to take study drug as follows:

- Weight-based RBV (as per Section 5.3.2).

If a subject forgets to take the medication at the correct time, it may be taken later in the day; however, no more than the protocol specified dose of SOF should be taken on any calendar day. The subject should resume the standing dosing schedule on the next day. Study medications should not be cut or split.

#### **5.5. Study Drug Compliance**

Subjects will be instructed to return any unused SOF and RBV in the original container on Day 7 (PK Lead-in) and/or at study treatment visits every 4 weeks (Treatment Phase).

Returned medication will be reconciled by the investigator in order to monitor the subject's compliance with the medication regimen.

#### **5.6. Prior and Concomitant Medications**

Concomitant medications taken within 30 days of Screening, up to and including the date of the visit four weeks after discontinuation of study treatment, need to be recorded in the source documents and eCRFs. All concomitant medications should be recorded in the source documents.

The following medications are prohibited from 28 days prior to the Day 1 visit through the end of treatment:

- Erythropoiesis-stimulating agents (ESAs); including but not limited to Procrit®, Aranesp® and Epogen®
- Granulocyte colony stimulating factor (GCSF)
- Chronic systemic immunosuppressant's including corticosteroids (prednisone equivalent of > 10 mg/day for > 2 weeks), azathioprine, or monoclonal antibodies (e.g., infliximab)
- Investigational agents or devices for any indication

- Drugs disallowed per prescribing information of REBETOL®
- Concomitant use of certain medications or herbal/natural supplements (inducers of drug transporters i.e. P-gp) with study drug(s) may result in pharmacokinetic interactions resulting in decreases in exposure of study drug(s). Representative medications which are excluded from 21 days prior to Day 1 through the end of treatment are listed below:

Drug	Agents Disallowed	Concomitant use with study drug may potentially result in changes of study drug concentration as listed below
Anticonvulsants	Phenobarbital, Phenytoin, Carbamazepine, Oxcarbazepine	Decrease in concentration of study drug
Antimycobacterials	Rifampin, rifabutine, rifapentine	Decrease in concentration of study drug
Herbal/Natural Supplements	St. John's Wort, Echinacea, Milk thistle (i.e., silymarin), Chinese herb sho-saiko-to (or Xiao-Shai-Hu-Tang)	Decrease in concentration of study drug

Medications for disease conditions **excluded** from the protocol (e.g., HIV-1 infection, active cancer, transplantation) are not listed under this Concomitant Medication section and are disallowed in the study.

## **6. STUDY PROCEDURES**

All subjects will complete screening, on-treatment and post-treatment assessments. Screening assessments will be completed within 28 days of the Day 1 visit. The end of study will occur at the 24-week Post-Treatment visit. The schedule of assessments is described below.

Information on the specific laboratory parameters to be measured and clinical assessments to be performed are provided in Section 6.6.

### **6.1. Subject Enrollment**

Each candidate's parent or legal guardian must sign an Informed Consent Form prior to the conduct of any screening procedures. Each study candidate who has the ability to read and write must sign an Assent Form, as required by IRB/IEC/local requirements, prior to the conduct of any study procedures. Screening evaluations will be used to determine the eligibility of each candidate for study enrollment. Candidates who fail to meet eligibility criteria by screening evaluations may be re-screened once  $\geq 30$  days after the initial screen if there is a reasonable expectation that the candidate will be eligible after repeat screening.

### **6.2. Screening Assessments**

#### **6.2.1. Screening Visit (Day -28 to Day 0)**

Subjects will complete all screening assessments within 28 days of the Day 1 visit. The screening window can be extended to 42 days for subjects requiring additional HCV GT testing or for extenuating circumstances.

The following procedures will be performed and documented:

- Written informed consent from parent or legal guardian and assent from subject, if applicable (see above)
- Medical history, including:
  - Hepatitis C history
  - Hepatitis C treatment history
  - Family history (i.e., height of parents, if known)
  - Liver biopsy results (if available)
- Complete physical examination
- Vital signs (temperature, blood pressure, pulse, respiratory rate), body weight and height

- Obtain blood samples for tests as listed in Section 6.6.1:
  - Hematology
  - Chemistry
  - Coagulation tests
  - HCV RNA
  - Determination of HCV viral GT and subtype
  - HCV antibody, HIV 1/2 antibody, and HBs antigen, HAV antibody
  - HbA1c
  - TSH
  - IL28B
  - Serum  $\beta$ -hCG pregnancy test for females of childbearing potential only
  - Alpha fetoprotein (AFP)
  - Alpha-1 anti-trypsin (ATT)
- Obtain urine sample for:
  - Urinalysis
  - Urine Drug Screen
- Review of concomitant medications
- Ask subject and/or parent/legal guardian if the subject is able to swallow and tolerate taking pills.
- Review of all inclusion and exclusion criteria
- Perform SOF swallowability assessment (for subjects administered SOF in tablet form only)

Subjects meeting all of the inclusion criteria and none of the exclusion criteria will return to the clinic for the Day 1 visit assessments.

### 6.3. PK Lead-in: Treatment Assessments

#### 6.3.1. Day 1

After confirmation of eligibility has been evaluated, the following tests and procedures must be completed prior to enrollment and dosing/dispensing on Day 1:

- Perform complete physical examination
- Tanner Pubertal Stage Assessment
- Vital signs, including body weight and height measurements
- A single X-ray of the left wrist, hand, and fingers for Bone Age Assessment
- Assessment of AEs and concomitant medications
- Pregnancy prevention counseling including partner pregnancy prevention for male participants (Subjects 12 to < 18 years of age and subjects < 12 years of age at the discretion of the Investigator based on subject's pubertal status)
- Obtain blood samples for:
  - Hematology
  - Chemistry
  - Coagulation tests
  - HCV RNA
  - Viral sequencing (archive)
  - PPD 
- Obtain urine samples for the following procedures:
  - Urinalysis
  - $\beta$ -hCG pregnancy test for females of childbearing potential only
- Subject completes quality of life survey: Subject is to review questionnaire with a parent/guardian and write/mark answers directly onto the questionnaire.

#### 6.3.1.1. Drug Administration

- Dispense study drugs as directed by the IWRS
- Instruct the subject on the appropriate RBV dose after weight-based dosage is calculated using Day 1 weight
- Instruct the subject on the packaging, storage and administration of all study drugs
- Perform SOF swallowability assessment (for subjects administered SOF in tablet form only if not previously completed at screening). Observe the subject taking the first dose of study drugs (with food) and record the time of first dose
- Subjects will be administered a dosing diary with instructions.

#### 6.3.2. Day 3

The following procedures/assessments are to be completed on Day 3:

- Perform a symptom-directed physical examination as needed
- Vital signs, including body weight and height
- Assessment of AEs and concomitant medications
- Review medication compliance with subject and/or parent/guardian
- Obtain blood samples for:
  - Hematology
  - Chemistry
  - HCV RNA
  - Viral sequencing (archive)
- Review subject dosing diary

#### 6.3.3. Day 7 – Intensive PK

The Day 7 Intensive PK visit should occur on the protocol-specified visit date based on the Day 1 visit. For the purposes of scheduling, the Day 7 Intensive PK visit may be performed within +3 days of the protocol-specified visit date (subjects will continue daily dosing through the Intensive PK Visit).

Subjects should come in a fasted state for the Day 7 Intensive PK visit (i.e., no food or drink except water at least 8 hours prior to the Day 7 Intensive PK visit). Subjects and/or parents/guardians should be instructed that the Day 7 dose of SOF+RBV must **not** be taken until the evaluations listed below are completed.

If the subject has already dosed prior to the Day 7 clinic visit or is **not** in a fasted state, the Day 7 intensive PK assessments must not be completed. The subject and/or parents/guardians should be instructed to return in a fasted state within 3 days (Days 8, 9, or 10) for the intensive PK visit.

If dosing non-compliance is identified as per subject dosing diary and pill count on or prior to the Day 7 visit, the Day 7 intensive PK assessments must not be completed. The subject and/or parents/guardians should be counseled regarding proper dosing and be scheduled to return for the Day 7 intensive PK visit no sooner than 3 days following compliant dosing and no later than Day 11 (i.e., return on Day 10 or Day 11). If dosing non-compliance is due to an AE, consultation with the Gilead Medical Monitor is required regarding the potential of rescheduling the Day 7 intensive PK visit.

In both scenarios described above, the subject and/or parents/guardians should be reminded not to take the SOF + RBV prior to arriving at the clinic on the day of the re-scheduled intensive PK visit. All Day 7 intensive PK assessments listed below should be completed when the subject returns.

The following evaluations are to be completed at the Day 7 Intensive PK visit:

- Perform a symptom-directed physical examination
- Vital signs, including body weight and height
- Assessment of AEs and concomitant medications
- Perform study drug accountability
- Review medication compliance with subject and/or parent/guardian.
- Obtain urine samples for the following procedures:
  - Urinalysis
  - Urine pregnancy test (females of childbearing potential only). If the urine pregnancy test is positive, the Intensive PK sampling will not be completed. The positive result will be confirmed with a serum pregnancy test.
- Obtain blood samples for the following laboratory analyses:
  - Hematology
  - Chemistry
  - Coagulation tests

- HCV RNA
- Viral sequencing (archive)
- Perform intensive PK sampling:
  - Blood samples will be collected at 0 (predose,  $\leq 30$  minutes prior to dosing). After collection of the predose sample, subjects will be provided a standardized meal. Within 5 minutes after consuming the standardized meal, subjects will be dosed with SOF + RBV per dosing requirements.
  - Post-dose blood samples will be collected as follows:
    - For Cohorts 1 and 2: 0.5, 1, 2, 3, 4, 8, and 12 hours post-dose (with predose also serving as  $t = 24$ ).
    - For Cohort 3 only: 2, 4, 8, and 12 hours post-dose (with predose also serving as  $t = 24$ ).
  - Subjects will be restricted from food intake until after collection of the 4-hour post dose blood sample, except for subjects in Cohort 3. Please also refer to the PK manual for details about standardized meals and PK sample processing instructions.

After completing the Day 7 intensive PK visit subjects will then continue to the Week 2 visit in Treatment Phase (described in Section 6.4.2) with no interruption in dosing.

#### **6.4. Treatment Phase: Treatment Assessments**

##### **6.4.1. Day 1**

After confirmation of eligibility has been evaluated, the following tests and procedures must be completed prior to enrollment and dosing/dispensing on Day 1:

- Perform complete physical examination
- Tanner Pubertal Stage Assessment
- Vital signs, including body weight and height measurements
- A single X-ray of the left wrist, hand, and fingers for Bone Age Assessment
- Review of AEs and concomitant medications

- Pregnancy prevention counseling including partner pregnancy prevention for male participants (Subjects 12 to < 18 years of age and subjects <12 years of age at the discretion of the Investigator based on subject's pubertal status).
- Obtain blood samples for:
  - Hematology
  - Chemistry
  - Coagulation tests
  - HCV RNA
  - Viral sequencing (archive)
  - PPD 
- Obtain urine sample for:
  - Urinalysis
  - $\beta$ -hCG pregnancy test for females of childbearing potential only
- Subject completes quality of life survey: Subject is to review questionnaire with a parent/guardian and write/mark answers directly onto the questionnaire.
- Perform SOF swallowability assessment (for subjects administered SOF in tablet form only if not previously completed at screening).
- For subjects receiving SOF oral granules, following drug administration assess palatability at Day 1, as applicable

#### 6.4.1.1. Drug Administration

- Dispense study drugs as directed by the IWRS
- Instruct the subject on the appropriate RBV dose after weight-based dosage is calculated using Day 1 weight
- Instruct the subject on the packaging, storage and administration of all study drugs
- Observe the subject taking the first dose of study drugs (with food) and record the time of first dose

**6.4.2. Weeks 1 and 2 ( $\pm$  3 days)**

Subjects who participated in the PK Lead-in will start study visits in Treatment Phase at Week 2. The following procedures/assessments are to be completed at these visits:

- Vital signs, including body weight and height measurements
- Perform symptom-directed physical examination
- Assessment of AEs and concomitant medications
- Obtain blood samples for:
  - Hematology
  - Chemistry
  - Coagulation tests
  - HCV RNA
  - Viral sequencing (archive)
  - Single PK

**6.4.3. Weeks 4 and 8 ( $\pm$  3 days)**

- Vital signs, including body weight and height measurements
- Perform symptom-directed physical examination
- Assessment of AEs and concomitant medications
- Obtain blood samples for
  - Hematology
  - Chemistry
  - Coagulation tests
  - HCV RNA
  - Viral sequencing (archive)
  - Single PK

- Obtain urine sample for:
  - $\beta$ -hCG pregnancy test for females of childbearing potential only
- Review medication compliance with subject and/or parent/guardian (subject should return all study drugs at these visits)
- Dispense study drugs as directed by the IWRS

#### **6.4.4. Week 12 ( $\pm$ 3 days)**

- Perform complete physical examination
- Tanner Pubertal Staging Assessment
- Vital signs, including body weight and height measurements
- Assessment of AEs and concomitant medications
- Pregnancy prevention counseling including partner pregnancy prevention for male participants (Subjects  $\geq$  12 years of age at the discretion of the Investigator based on subject's pubertal status)
- Obtain blood samples for:
  - Hematology
  - Chemistry
  - Coagulation tests
  - HCV RNA
  - Viral sequencing (archive)
  - TSH
  - Single PK
- Obtain urine sample for:
  - $\beta$ -hCG pregnancy test for females of childbearing potential only
- Subject completes quality of life survey: Subject is to review questionnaire with a parent/guardian and write/mark answers directly onto the questionnaire. (GT-2 Subjects only)
- Review medication compliance with subject and/or parent/guardian.

- Dispense study drugs as directed by the IWRS (GT-3 Subjects Only)
- GT-2 Subjects should return all bottles and kits at the Week 12 Visit

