**Treatment Phase:**

- **GT-2 Subjects:** Study visits for GT-2 subjects will occur at Day 1, and the end of Weeks 1, 2, 4, 8, and 12.
- **GT-3 Subjects:** Study visits for GT-3 subjects will occur at Day 1, and the end of Weeks 1, 2, 4, 8, 12, 16, 20, and 24.

All Treatment Phase subjects will then return for follow-up visits at 4, 12 and 24 weeks after discontinuation of therapy.

On-treatment assessments will include physical examination, vital signs (including height and weight) adverse events, concomitant medications, pregnancy prevention counseling (all subjects  $\geq$  12 years of age and subjects < 12 years of age at the discretion of the Investigator based on subject's pubertal status), safety laboratory tests, coagulation tests, HCV RNA, PK samples, a quality of life survey and urine pregnancy tests (females of childbearing potential only). Tanner Pubertal Stage assessment will be performed at Day 1 and end of treatment visits; parental heights will be recorded at Day 1. The Bone Age Assessment will be performed at Day 1 visit. If available, results from liver biopsies will be collected at screening. SOF swallowability assessment with placebo will be performed (if not performed at screening) on Day 1 to assess a subject's ability to swallow a 400 mg or 100 mg SOF tablet For subjects continuing from the PK Lead-in, the screening, Day 1 and Week 1 visits of the Treatment Phase will not be required. Samples for viral RNA sequencing/phenotyping will be collected at Day 1 and every visit thereafter.

Post-treatment assessments will include adverse events, concomitant medications, vital signs (including body weight and height), symptom-directed physical examination, safety laboratory tests, HCV RNA, Tanner Pubertal Stage assessment (only post-treatment Week 12 and post-treatment Week 24), Bone Age Assessment (only post-treatment Week 24) and urine pregnancy tests as defined in [Appendix 5](#).

Palatability of SOF oral granules will be assessed at Day 1, as applicable.

PPD

---

**Test Product, Dose,  
and Mode of  
Administration:**

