### 1.3. Ribavirin (RBV)

Ribavirin is a guanosine analogue that inhibits the in vitro replication of a wide range of RNA and DNA viruses {15572}, {15668}. Ribavirin monotherapy has little or no effect on the replication of HCV but can result in normalization of serum ALT activity and improvement in liver histology. When combined with interferon or PEG therapy, RBV decreases substantially the relapse rate seen after cessation of interferon therapy {12557}, {12558}.

Ribavirin is a known teratogen (FDA category X). Furthermore, RBV is known to accumulate intracellularly where it is cleared slowly, and is also excreted in semen. Therefore, extreme care must be taken to avoid pregnancy during RBV therapy and for up to 7 months following completion of treatment. A comprehensive review of RBV is contained in the package insert/SmPC.

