**6.4.6. Week 24 ( $\pm$  3 days) – GT-3 Subjects only**

- Perform complete physical examination
- Tanner Staging Assessment
- Vital signs, including body weight and height measurements
- Assessment of AEs and concomitant medications
- Pregnancy prevention counseling including partner pregnancy prevention for male participants (Subjects 12 to < 18 years of age and subjects < 12 years of age at the discretion of the Investigator based on subject's pubertal status)

- Obtain blood samples for:
  - Hematology
  - Chemistry
  - Coagulation tests
  - HCV RNA
  - Viral sequencing (archive)
  - TSH
  - Single PK
- Obtain urine sample for:
  - $\beta$ -hCG pregnancy test for females of childbearing potential only
- Subject completes quality of life survey: Subject is to review questionnaire with a parent/guardian and write/mark answers directly onto the questionnaire
- Review medication compliance with subject and/or parent/guardian.
- GT-3 Subjects should return all bottles and kits at the Week 24 Visit

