**Appendix Table 2. Treatment Phase: Screening and On-Treatment Study Visits**

	Screening c	Day 1 c	Visit identified by on-treatment study week								Early Termination
			1 c	2	4	8	12 g	16 g	20 g	24 g	
Clinical Assessments											
Informed Consent / Assent	X										
Determine Eligibility	X	X									
Medical History	X										
Complete Physical Examination	X	X					X			X	X
Symptom-Directed Physical Examination			X	X	X	X		X	X		
Tanner Pubertal Stage Assessment		X					X			X	X
Vital Signs a	X	X	X	X	X	X	X	X	X	X	X
Bone Age Assessment		X									
AEs and Concomitant Medications	X	X	X	X	X	X	X	X	X	X	X
Pregnancy Prevention Counseling h		X					X			X	X
SOF Swallowability Assessment	X	X j									
Quality of Life Survey e		X					X			X	X
Review of Study Medication Compliance					X	X	X	X	X	X	X
Study Drug Dispensing b		X			X	X	X i	X i	X i		

	Screening c	Day 1 c	Visit identified by on-treatment study week								Early Termination	
			1 c	2	4	8	12 g	16 g	20 g	24 g		
Laboratory Assessments												
Hematology, Chemistry Coagulation	X	X	X	X	X	X	X	X	X	X	X	X
HCV RNA	X	X	X	X	X	X	X	X	X	X	X	X
Viral Sequencing d		X	X	X	X	X	X	X	X	X	X	X
Serum or Urine Pregnancy Testing	X	X			X	X	X	X	X	X	X	X
Single PK			X	X	X	X	X	X	X	X	X	X
PPD												
Urinalysis	X	X										
Urine Drug Test	X											
HCV Genotyping, IL28B	X											
HCV antibody, HIV 1/2 antibody, HBs antigen, HAV antibody	X											
HbA1c	X											
TSH	X						X			X		X
Alpha fetoprotein, Alpha-1 anti-trypsin	X											
Palatability Assessment of Oral Granules k		X										

a Vital signs include blood pressure, pulse, respiratory rate and temperature, body weight and height

b The IWRS will provide direction on the specifics of each subject's study drug dispensing.

c Subjects rolling over from PK Lead-in will not be required to repeat screening, Day 1 or Week 1 visits during the on Treatment Phase

d Plasma samples will be collected and stored for potential HCV sequencing and other virology studies

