e Quality of life survey will be completed at Day 1, Week 12 (only GT-2 subjects), Week 24 (only GT-3 subjects) and Early Termination if a site is approved to use the survey. Subject is to review questionnaire with a parent/guardian and write/mark answers directly onto the questionnaire.

f **PPD**

g GT-2 subjects will complete through the Week 12 visit; GT-3 subjects will complete through the Week 24 visit.

- h Including partner pregnancy prevention for male participants (subjects 12 to < 18 years of age and subjects < 12 years of age at the discretion of the Investigator based on subject's pubertal status).
- i Study Drug Dispensing at the Week 12, Week 16, and Week 20 visit for GT-3 subjects only
- j Swallowability can occur at Day 1 if not completed during screening.
- k Palatability of SOF oral granules will be assessed at Day 1, applicable.

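### Protocol Section 6.4.4 gives a different rule for who receives pregnancy-prevention counselling at Week 12 from the synopsis, Appendix Table 2 and the six other visit sections that list it

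*Protocol*

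**What the plan says.** Section 6.4.4 (Week 12) includes a counselling item that covers partner pregnancy prevention for male participants. Its population is subjects aged ≥ "12 years of age at the discretion of the Investigator based on subject's pubertal status". No other age group appears in that item.

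Appendix Table 2 marks counselling at Day 1, Week 12, Week 24 and Early Termination, all under footnote h. That footnote names "subjects 12 to < 18 years of age and subjects < 12 years of age at the discretion of the Investigator", with pubertal status as the basis for the discretion. The SAP's copy of the table (SAP Appendix 1) carries the same footnote.

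The synopsis, in its Treatment Phase on-treatment assessments, refers to all subjects aged ≥ "12 years of age and subjects < 12 years of age at the discretion of the Investigator based on subject's pubertal status". Section 6.4.6 (Week 24) has "Subjects 12 to < 18 years of age and subjects < 12 years of age at the discretion of the Investigator".

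Two further statements bear on the weight of the point. Section 1.3 describes ribavirin as teratogenic and says that "extreme care must be taken to avoid pregnancy during RBV therapy and for up to 7 months following completion of treatment". Footnote g of Appendix Table 2 says that "GT-2 subjects will complete through the Week 12 visit", which makes Week 12 the end-of-treatment visit for that genotype.

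**The concern.** Two operative parts of the protocol describe the same activity at the same visit and give different populations. Section 6.4.4 differs in two respects: it makes counselling of the older group discretionary, and it leaves the younger group out of the counselling line.

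Staff may work from the Section 6 visit text or from the schedule table. A site using only Section 6.4.4 could decide not to counsel an adolescent at Week 12 and still be following that section. A site using Appendix Table 2 would counsel every subject aged 12 to < 18 and consider the younger ones. A monitor would have no single standard for judging whether a Week 12 session had been missed.

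The visit matters. For GT-2 subjects it is where treatment ends and the post-ribavirin contraception period begins. For GT-3 subjects it is the only scheduled counselling between the first and last on-treatment visits. The length of the post-treatment period is a separate matter and is not part of this point.

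**Working it through.** No formula applies; this is a comparison of texts. The places that say who is counselled are:

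| Place | Aged 12 and over | Under 12 |
|---|---|---|
| Synopsis, PK Lead-in and Treatment Phase | All | At discretion |
| Section 6.3.1, PK Lead-in Day 1 | Named, no discretion | At discretion |
| Section 6.4.1, Treatment Phase Day 1 | Named, no discretion | At discretion |
| **Section 6.4.4, Week 12** | **At discretion** | **Not mentioned** |
| Section 6.4.6, Week 24 | Named, no discretion | At discretion |
| Section 6.4.7, Early Termination | Named, no discretion | At discretion |
| Section 6.5.1, post-treatment Week 4 | Named, no discretion | At discretion |
| Section 6.5.2, post-treatment Week 12 | Named, no discretion | At discretion |
| Appendix Table 2 footnote h, and its SAP copy | Named, no discretion | At discretion |

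**Count.** Seven visit sections list counselling. Six share one rule; Section 6.4.4 is the seventh. Day 3, Day 7, Weeks 1, 2, 4, 8, 16 and 20, and post-treatment Week 24 list no counselling, so they neither agree nor conflict.

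**Is the common wording itself clear?** The Day 1 phrase, "Subjects 12 to < 18 years of age and subjects <12 years of age at the discretion of the Investigator", could with some strain be read as attaching the discretion to both age groups. The synopsis rules that out by writing all subjects for those aged 12 and over. Even on the strained reading, Section 6.4.4 would still differ by omitting the under-12s.

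**Interval between scheduled sessions, for subjects who complete treatment:**

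- GT-2: Day 1, Week 12, then post-treatment Week 4, which is 12 + 4 = 16 weeks from the start. Without the Week 12 session, the interval from Day 1 to the next session is about 16 weeks instead of 12 and then 4.
- GT-3: Day 1, Week 12, Week 24. Without the Week 12 session there is one interval of 12 + 12 = 24 weeks, all on ribavirin.

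**Who is exposed to the discrepancy.** The discretionary wording applies to adolescents who reach Week 12. The plan is to enrol about 50 adolescents, which is an approximate ceiling on those to whom the line applies and not an estimate of missed sessions. The documents do not give the number of pubertal children under 12 or the expected split by genotype.

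**The case against.** The strongest case on the other side is that this is a drafting slip with little practical effect. Most of its elements stand.

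- **The texts are compatible in practice.** A reader might infer that a site cannot follow both. That is not supported. Section 6.4.4 permits counselling of adolescents and does not exclude younger children, so a site that follows footnote h breaches nothing in Section 6.4.4. The two differ in what they require.
- **It looks accidental.** A reader might take Section 6.4.4 as a deliberate Week 12 rule. Nothing in the documents suggests that. Removing the middle phrase about subjects under 12 from the synopsis wording leaves essentially the Section 6.4.4 wording, and a pubertal-status criterion fits the younger group more naturally. Dropped words are a likely explanation, though the text cannot prove it.
- **Girls under 12 are not ignored at this visit.** Appendix 5 treats post-menarchal females as of childbearing potential with no lower age limit, apart from documented ovarian failure or sterilisation. Section 6.4.4 itself requires a urine pregnancy test for females of childbearing potential. Only its counselling line fails to mention the under-12s.
- **Other safeguards exist.** Section 6.6.12 requires pregnancy testing every 4 weeks during dosing and for at least 6 months after ribavirin. Appendix 5 sets contraception commitments to 6 months after the last ribavirin dose for females and 7 months for males, and Section 4.3 excludes sexually active subjects unwilling to use contraception. Counselling under the common wording also takes place at Day 1 and at post-treatment Weeks 4 and 12.

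These arguments limit the consequences but leave the discrepancy in place. Pregnancy testing detects a pregnancy after the event and does not cover male subjects, whereas the counselling item includes partner pregnancy prevention and Section 3.4 lists partner pregnancy as a reason to stop study medication.

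**Conclusion.** The point holds as an internal inconsistency confined to one visit. Section 6.4.4 differs from the synopsis, from footnote h for the same visit and from all six other visit sections that list counselling, and it differs for both age groups. The realistic consequence is that a site relying on Section 6.4.4 alone omits a session for some adolescents, or is not prompted to consider a pubertal child under 12. That lengthens the interval between scheduled sessions to about 16 weeks for GT-2 or 24 weeks for GT-3.

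How often this would happen cannot be estimated from the documents. No endpoint, analysis set, test or sample-size figure depends on it. The point merits correction because the text is operative, the drug is one for which the protocol asks for particular care, and the correction is very small.

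The conclusion assumes that the Section 6.4.4 sentence reads this way in the approved protocol. If the missing words are present there, the point falls away. It takes no position on which counselling rule is clinically right.

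**What to change.** Check the Section 6.4.4 counselling item against the approved protocol. If it reads as above, reconcile it with the synopsis and Appendix Table 2 footnote h so that one rule states who is counselled at Week 12, for subjects aged 12 and over and for those under 12. The choice of rule belongs to the sponsor and its clinical advisers. The cost is about one line of protocol text, with a note to sites so that visit checklists match. No change to the SAP's analyses follows; its copy of the schedule needs attention only if footnote h is the text that changes.
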